**Caution: Investigational Device. Limited by Federal Law (USA) to Investigational Use.**

In addition, the following statements appear on the product labeling.

**CAUTION: Exclusively for Clinical Investigations.**

Device labeling will be provided in local language(s) as per respective national regulations.

### 5.3.2. Control Device

Information is provided in the IFU supplied with the commercially available CoreValve® or CoreValve® Evolut™ R System (if used because a center no longer has access to CoreValve).

## 6. Objectives

The objective of the REPRISE III trial is to evaluate the safety and effectiveness of the Lotus™ Valve System and LOTUS Edge™ Valve System for transcatheter aortic valve replacement (TAVR) in symptomatic subjects with calcific, severe native aortic stenosis who are considered at extreme or high risk for surgical valve replacement.

## 7. Endpoints

Outcomes will be assessed on an intention-to-treat (ITT) basis, an implanted basis, and an as-treated basis. The ITT analysis population of the randomized cohort includes subjects who sign an Informed Consent Form (see Section 0), are enrolled in the trial (see Section 10.1 for point of enrollment), and are randomized, whether or not an assigned study device is implanted. The implanted analysis population includes ITT subjects who are implanted with an assigned, randomized study device. The as-treated population includes subjects who sign an Informed Consent Form, are enrolled in the trial, are randomized, and received a study device, with the analysis based on the treatment actually received. For all analysis sets, if a subject receives 2 valves, the subject is assigned to the group corresponding to the first valve received. Among the roll-in (initial cohort with 23 mm, 25 mm, and 27 mm Lotus Valve System and subsequent cohort with 29 mm LOTUS Edge Valve System), Lotus 21 mm Nested Registry, LOTUS Edge Nested Registry, LOTUS Edge 29 mm Nested Registry, and U.S. Continued Access Study cohorts, for ITT analyses, all subjects who sign the IRB/IEC-approved study ICF and are enrolled in the trial will be included in the analysis sample, regardless of whether the study device was implanted. For these cohorts, the as-treated population includes all subjects implanted with the Lotus/LOTUS Edge valve. Endpoint definitions can be found in Table 26.2-1.

### 7.1. Primary Endpoints

#### 7.1.1. Primary Safety Endpoint

The primary safety endpoint is a composite of all-cause mortality, stroke, life-threatening and major bleeding events, stage 2 or 3 acute kidney injury, or major vascular complications at 30 days. The primary analysis set for the primary safety endpoint is the implanted analysis set.

### 7.1.2. Primary Effectiveness Endpoint

The primary effectiveness endpoint is a composite of all-cause mortality, disabling stroke, or moderate or greater paravalvular aortic regurgitation (based on core lab assessment) at 1 year. The primary analysis set for the primary effectiveness endpoint is the implanted analysis set.

### 7.1.3. Secondary Endpoint

The secondary endpoint is the rate of moderate or greater paravalvular aortic regurgitation based on core lab assessment at 1 year. The primary analysis set for the secondary endpoint is the ITT analysis set.

## 7.2. Additional Measurements

Additional measurements based on the VARC endpoints and definitions (see **Note 1** below) will be collected peri- and post-procedure, at discharge or 7 days post-procedure (whichever comes first), 30 days, 6 months, and 1, 2, 3, 4, and 5 years post index procedure, unless otherwise specified below.

- Safety endpoints (see **Note 2** below) adjudicated by an independent Clinical Events Committee (CEC; Section 22.1.1):
  - Mortality: all-cause, cardiovascular, and non-cardiovascular
  - Stroke: disabling and non-disabling
  - Myocardial infarction (MI): periprocedural ( $\leq 72$  hours post index procedure) and spontaneous ( $> 72$  hours post index procedure)
  - Bleeding: life-threatening (or disabling) and major
  - Acute kidney injury ( $\leq 7$  days post index procedure): based on the AKIN System Stage 3 (including renal replacement therapy) or Stage 2
  - Major vascular complication
  - Repeat procedure for valve-related dysfunction (surgical or interventional therapy)
  - Hospitalization for valve-related symptoms or worsening CHF (NYHA class III or IV)
  - New permanent pacemaker implantation resulting from new or worsened conduction disturbances (definitions in Table 26.2-1; see **Note 3** below)
  - New onset of atrial fibrillation or atrial flutter
  - Coronary obstruction: periprocedural ( $\leq 72$  hours post index procedure)
  - Ventricular septal perforation: periprocedural ( $\leq 72$  hours post index procedure)
  - Mitral apparatus damage: periprocedural ( $\leq 72$  hours post index procedure)
  - Cardiac tamponade: periprocedural ( $\leq 72$  hours post index procedure)
  - Prosthetic aortic valve malpositioning, including valve migration, valve embolization, or ectopic valve deployment
  - Transcatheter aortic valve (TAV)-in-TAV deployment

- Prosthetic aortic valve thrombosis
- Prosthetic aortic valve endocarditis
- Device performance endpoints peri- and post-procedure:
  - Successful vascular access, delivery and deployment of the study valve and successful retrieval of the delivery system
  - Successful retrieval of the study valve if retrieval is attempted
  - Successful repositioning of the study valve if repositioning is attempted (see **Note 4** below)
  - Grade of aortic valve regurgitation: paravalvular, central and combined; the overall distribution of paravalvular aortic regurgitation (none, trace/trivial, mild, moderate, severe) will be determined as well as the percentage of subjects who have moderate or severe paravalvular regurgitation and the percentage of subjects who have mild, moderate or severe paravalvular regurgitation
- Clinical procedural success (30 days), defined as implantation of the study device in the absence of death, disabling stroke, major vascular complications, and life-threatening or major bleeding
- Procedural success (30 days), defined as absence of procedural mortality, correct positioning of a single transcatheter valve into the proper anatomical location, intended performance of the study device (effective orifice area [EOA]  $>0.9 \text{ cm}^2$  for BSA  $<1.6 \text{ m}^2$  and EOA  $>1.1 \text{ cm}^2$  for BSA  $\geq 1.6 \text{ m}^2$  plus either a mean aortic valve gradient  $<20 \text{ mm Hg}$  or a peak velocity  $<3 \text{ m/sec}$ , and no moderate or severe prosthetic valve aortic regurgitation) plus no serious adverse events at 30 days
- Additional indications of prosthetic aortic valve performance as measured by transthoracic echocardiography (TTE; see **Note 5** below) and assessed by an independent core laboratory, including effective orifice area, mean and peak aortic gradients, peak aortic velocity, and grade of aortic regurgitation (see **Note 6** below).
- Modified device success (30 days), reported for subjects randomized and implanted with an assigned study device and defined as follows: absence of mortality with the originally implanted transcatheter valve in the proper anatomical location, no additional aortic valve procedures, and with the intended performance of the prosthetic valve (either a mean aortic valve gradient  $<20 \text{ mm Hg}$  or a peak velocity  $<3 \text{ m/sec}$  with no moderate or severe prosthetic valve aortic regurgitation)
- Functional status as evaluated by the following:
  - 5-m gait speed test (at 1 year compared to baseline)
  - New York Heart Association (NYHA) classification
- Neurological status (see **Note 7** below) as determined by the following:
  - Neurological physical exam by a neurologist, neurology fellow, neurology physician assistant, or neurology nurse practitioner at discharge and 1 year
  - National Institutes of Health Stroke Scale (NIHSS) at discharge and 1 year

- Modified Rankin Scale (mRS) at all time points
- Health status as evaluated by Kansas City Cardiomyopathy and SF-12 Quality of Life (QOL) questionnaires at baseline; 1 and 6 months; and 1, 3, and 5 years
- Resource utilization associated with the procedure and/or follow-up.

Additionally, assessment of leaflet thickening and mobility using 4D CT will be carried out at 30 days and 1 year post index procedure for subjects in the CT Imaging Substudy of the U.S. Continued Access Study. The CT scans will be evaluated by an independent CT Core Laboratory and should be blinded to local investigators for cardiac valve findings (local reading should be only for non-cardiac valve findings such as unexpected lung pathology; see Section 11.10.1 for additional information).

**Note 1:** The most current VARC definitions and endpoints available at the beginning of the trial were used.

**Note 2:** The VARC-2 safety composite at 30 days includes all-cause mortality, all stroke (disabling and non-disabling), life-threatening bleeding, acute kidney injury (Stage 2 or 3), coronary artery obstruction requiring intervention, major vascular complication, and repeat procedure for valve-related dysfunction. The VARC-2 time-related valve safety composite includes structural valve deterioration (valve-related dysfunction requiring repeat procedure [TAVR or SAVR]), prosthetic valve endocarditis, prosthetic valve thrombosis, thromboembolic events (e.g., stroke), and VARC bleeding (unless clearly unrelated to valve therapy based on investigator assessment)

**Note 3:** Clinical indications for permanent pacemaker implantation are outlined in the ACCF/AHA/HRS Guidelines for Device-Based Therapy of Cardiac Rhythm Abnormalities. Permanent pacemaker implantation should generally be performed only for accepted Class I indications.

**Note 4:** For the Lotus Valve System, repositioning may be achieved with partial or full resheathing of the valve; the proportion of subjects with partial valve resheathing and full valve resheathing will be determined.

**Note 5:** At least 1 echocardiogram must be obtained before discharge or 7 days (whichever comes first); if multiple echocardiographic studies are performed prior to discharge and within 7 days of the procedure, the latest study performed will be used for analysis.

**Note 6:** The VARC-2 clinical efficacy composite (after 30 days) includes all-cause mortality, all stroke, required hospitalization for valve-related symptoms or worsening CHF (NYHA class III or IV), and prosthetic heart valve dysfunction (mean aortic valve gradient  $\geq 20$  mmHg, effective orifice area  $\leq 0.9$ - $1.1$  cm^2 and/or Doppler velocity index [DVI]  $< 0.35$ , AND/OR moderate or severe prosthetic valve aortic regurgitation [per VARC definition]). The need for hospitalization associated with valve-related symptoms or worsening CHF serves as a basis for calculation of a “days alive outside the hospital” endpoint. This includes heart failure, angina, or syncope due to aortic valve disease requiring intervention or intensified medical management; clinical symptoms of CHF with objective signs including pulmonary edema, hypoperfusion, or documented volume overload AND administration of

intravenous diuresis or inotropic therapy, performance of aortic valvuloplasty, institution of mechanical support (intra-aortic balloon pump or ventilation for pulmonary edema), or hemodialysis for volume overload; clear documentation of anginal symptoms AND no clinical evidence that angina was related to coronary artery disease or acute coronary syndrome; documented loss of consciousness not related to seizure or tachyarrhythmia.

**Note 7:** For subjects diagnosed with a neurological event (e.g., stroke, transient ischemic attack), a neurological physical exam (conducted by a neurologist, neurology fellow, neurology physician assistant, or neurology nurse practitioner), NIHSS assessment, and mRS must be performed after the event. Additionally, mRS must be administered at 90±14 days post-neurological event (see Table 11.1-1). If a subject who has not received a study device (investigational or control) experiences a neurological event within the first 1 year after the index procedure, mRS must be performed on that subject after the event and at 90±14 days post-neurological event and the results must be reported to the Sponsor.

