#### **11.7.1. Medtronic CoreValve (Control) Cohort**

The IFU associated with the control device (CoreValve) should be followed. A final post-deployment aortogram of the ascending aorta must be performed and forwarded to the Core Laboratory with the procedural cine-angiogram for analysis.

Labels from devices used during the procedure (e.g., CoreValve, Introducer, etc.) should be retained so that they can be included in the appropriate source documents and reported in the eCRFs. During the procedure, designated center study personnel must capture necessary information on acute device/delivery system performance and procedure. The following information will be collected during the procedure.

- Date of procedure
- Specifics of device type (such as size and model)

- Time of first vascular puncture (femoral) and time of vascular closure (skin-to-skin time)
- Introducer insertion and removal time
- Descriptive information on balloon valvuloplasty (e.g., size of balloon, number of balloon inflations)
- Any devices used and adjunctive procedures performed during implant procedure
- Heart rhythm after balloon valvuloplasty with rhythm strip should be recorded (12-lead ECG is not required).
- Valve catheter insertion and removal time
- Descriptive information on valve implantation procedure
- Adverse event (AE) assessment and associated treatment (including AE, serious adverse event [SAE], serious adverse device effect [SADE], unanticipated adverse device effect [UADE]/unanticipated serious adverse device effect [USADE], adverse device effect [ADE] and Clinical Events Committee [CEC] events; see Section 21).
- Device deficiencies assessment

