For the randomized cohort, event reporting (eCRF) is required beginning from the time of randomization.

For the roll-in, Lotus 21 mm Nested Registry, LOTUS Edge Nested Registry, roll-in with the 29 mm LOTUS Edge, LOTUS Edge 29 mm Nested Registry, and U.S. Continued Access Study cohorts, event reporting (eCRF) is required beginning from the time an attempt is made to insert the Lotus Valve System/LOTUS Edge Valve System into the subject's femoral artery.

Refer to Section 19 for the known risks associated with the study devices (test and control). Based on the VARC recommendations and definitions, the adverse events and/or safety endpoints requiring adjudication by the CEC include the following.

- Mortality: all-cause, cardiovascular, and non-cardiovascular
- Stroke: disabling and non-disabling
- Myocardial infarction (MI): periprocedural ( $\leq 72$  hours post index procedure) and spontaneous ( $> 72$  hours post index procedure)
- Bleeding events: life-threatening (or disabling) and major
- Acute kidney injury ( $\leq 7$  days post index procedure): based on the AKIN System Stage 3 (including renal replacement therapy) or Stage 2
- Vascular complications: major
- Repeat procedure for valve-related dysfunction (surgical or interventional therapy)
- Hospitalization for valve-related symptoms or worsening congestive heart failure (NYHA class III or IV)
- New permanent pacemaker implantation resulting from new or worsened conduction disturbances
- New onset of atrial fibrillation or atrial flutter
- Coronary obstruction: periprocedural ( $\leq 72$  hours post index procedure)
- Ventricular septal perforation: periprocedural ( $\leq 72$  hours post index procedure)
- Mitral apparatus damage: periprocedural ( $\leq 72$  hours post index procedure)
- Cardiac tamponade: periprocedural ( $\leq 72$  hours post index procedure)
- Prosthetic aortic valve malpositioning, including valve migration, valve embolization, or ectopic valve deployment
- TAV-in-TAV deployment
- Prosthetic aortic valve thrombosis
- Prosthetic aortic valve endocarditis

Details on the CEC events and procedures are outlined in the CEC charter. Tests and images required to adjudicate these events are specified in the event definitions (see Table 26.2-1).

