### **21.2. Relationship to Study Device(s)**

The Investigator must assess the relationship of the AE/SAE to the study device as related or unrelated. See criteria in Table 21.2-1.

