#### **22.1.1. Clinical Events Committee**

A CEC will be used in this study. A CEC is an independent group of individuals with pertinent expertise, including cardiovascular interventional therapy, cardiovascular surgery, and neurology, which reviews and adjudicates important endpoints and relevant adverse events reported by study investigators. The CEC will review a safety event dossier, which may include copies of subject source documents provided by study sites, and adjudicate study endpoint related clinical events. The responsibilities, qualifications, membership, and committee procedures of the CEC are outlined in the CEC charter.

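### In the VARC-2 time-related valve safety composite, an additional measurement, an investigator who knows the implanted device decides which bleeds are dropped as unrelated

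*Combined protocol and SAP*

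**What the plan says.** Section 7.2 of the protocol lists safety endpoints "adjudicated by an independent Clinical Events Committee (CEC; Section 22.1.1"), among them "Bleeding: life-threatening (or disabling) and major", and attaches Note 2 to that heading. Section 21.1 repeats the arrangement: "the adverse events and/or safety endpoints requiring adjudication by the CEC include the following", with "Bleeding events: life-threatening (or disabling) and major" on the list.

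Note 2 defines two VARC-2 composites. The time-related valve safety composite joins structural valve deterioration, prosthetic valve endocarditis, prosthetic valve thrombosis, thromboembolic events and "VARC bleeding (unless clearly unrelated to valve therapy based on investigator assessment"). The default is that a bleed counts. It leaves the composite only on the investigator's judgement that it is clearly unrelated.

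On relatedness in general, Section 21.2 says: "The Investigator must assess the relationship of the AE/SAE to the study device as related or unrelated". Section 22.1.1 describes the CEC as a group that "reviews and adjudicates important endpoints and relevant adverse events reported by study investigators" and leaves its procedures to a charter.

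**The concern.** Two judgements determine whether a bleed enters this composite: whether it occurred at the stated severity, and whether it is clearly unrelated to valve therapy. For life-threatening and major bleeds the first goes to an independent committee. The second, which is the only one that can remove an adjudicated bleed, goes to the investigator. The trial compares an investigational valve with a commercial one, and the person judging relatedness knows which was used.

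Relatedness is hard to judge in patients on antiplatelet or anticoagulant therapy, and the protocol gives no criteria for what is clearly unrelated to valve therapy. The criteria in Table 21.2-1 concern the investigational product, so they do not carry over evenly to the control arm. If the threshold for dropping a bleed differed by arm, the composite could show a difference in valve safety that is not there, or hide one that is. Bleeding is also where the exclusion has most to act on: in the earlier single-arm Lotus study (Table 4.1-4, full cohort, 1 year) major bleeding was 23.3% and life-threatening bleeding 9.2%, against 8.4% for all stroke, 1.2% for valve thrombosis and 0.8% for endocarditis.

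**Working it through.** No figure in the plan depends on this composite, so there is nothing to reproduce. The check is textual, followed by a bounding calculation.

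**Who decides what**
- Occurrence of a life-threatening or major bleed: the CEC (Sections 7.2 and 21.1).
- Removal of a bleed from the composite: the investigator (Section 7.2, Note 2).
- CEC power to confirm or overrule that removal: none stated. Section 22.1.1 does not mention relatedness, and Section 21.2 gives device relatedness to the investigator.
- Minor bleeds: the bleeding definition in Table 26.2-1 includes them and Note 2 sets no severity limit, but they are on neither CEC list. If they count, neither judgement on them has stated CEC review.

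**Does the investigator know the arm?** The protocol never says so in words, but it follows. For the control arm, Section 11.7.1 says: "The IFU associated with the control device (CoreValve) should be followed". Section 11.7.2 sets out a separate Lotus procedure, and Section 11.10.3 requires rotational X-ray only for Lotus recipients. The blinding described for local investigators covers only valve findings on CT in a single-arm substudy. Section 12.2.2 relies on core laboratories, which do not judge bleeding.

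**Which analyses are affected?** Section 12.1 tests primary safety, primary effectiveness and the secondary endpoint. The primary safety endpoint counts life-threatening and major bleeding without a relatedness exception (Section 7.1.1). The other two contain no bleeding component. Section 12.1.5 plans no inference on additional measurements, yet still compares the randomized arms on them with tests and 95% confidence intervals.

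**Size.** Let b be the true proportion of subjects with a bleed, equal in both arms, and d the proportion of those dropped. The bleeding contribution in an arm is b(1 − d), so the spurious difference is b × (d_A − d_B).

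- Input b: the 1-year rates in Table 4.1-4 are 58/249 = 23.3% (major) and 23/249 = 9.2% (life-threatening). Full overlap gives 23.3%; no overlap gives 23.3 + 9.2 = 32.5%. The range used is 25% to 32.5%.
- Input d: the documents give none. The values 20% v 10% and 15% v 10% are assumptions.

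| Bleeding b | 20% v 10% dropped | 15% v 10% dropped |
|---|---|---|
| 25% | 0.25 × 0.10 = 2.5 points | 0.25 × 0.05 = 1.25 points |
| 32.5% | 0.325 × 0.10 = 3.25 points | 0.325 × 0.05 = 1.6 points |

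At full overlap (23.3%) the two results would be 2.3 and 1.2 points.

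These are upper values for each scenario. The formula assumes that every subject with a dropped bleed leaves the composite, but one who also had a stroke, endocarditis, thrombosis, structural deterioration or another retained bleed stays in.

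If the differing thresholds applied only to bleeds after 30 days, b is much smaller. From 30 days to 1 year in Table 4.1-4, major bleeding rises from 53 to 58 subjects and life-threatening from 18 to 23, so at most 5 + 5 = 10 are newly counted: 10/249 = 4.0%. Then 0.04 × 0.10 = 0.4 points and 0.04 × 0.05 = 0.2 points. This is a low case, not a ceiling: Section 4.1.2 reports two life-threatening bleeds within 30 days in the feasibility study that were held unrelated to valve implantation.

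**The case against.** The strongest reply is that the protocol does not contradict itself. A reader might infer from Note 2 that the investigator overrides the CEC. The text does not support that: the CEC lists name individual events and do not include this composite, and relatedness is a separate judgement that Section 21.2 gives to investigators for devices generally. This stands. The point is a design choice about who makes the second judgement.

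A reader might also infer that the trial's safety conclusion is exposed. It is not. Primary safety has no relatedness filter, and life-threatening and major bleeding are also collected separately as CEC-adjudicated endpoints through 5 years. Anyone can compare unfiltered bleeding by arm. That would help to reveal differential dropping, but it does not give the composite without the filter, because overlap with the other components is unknown.

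Third, the discretion is narrow: a bleed counts unless clearly unrelated. That should keep drop rates down, although the term is left without criteria. Fourth, the assumed drop rates alone create the calculated effect, and nothing in the documents shows that dropping would differ by arm. That also stands, so the figures are bounds on assumptions and not estimates.

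Finally, the CEC charter was not among the documents and might give the CEC this role, and Note 2 may follow the published VARC-2 definition. Neither can be checked here. If the wording is part of that definition, changing the assessor would depart from it, which is a reason to report an all-bleeds version as well.

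**Conclusion.** The point holds, with limited reach. As written, an assessor who knows the implanted device can remove a bleed from the time-related valve safety composite with no stated independent check, and the arms will be compared on it. Given 1-year bleeding of 25% to 32.5% in both arms and the assumed drop rates, the distortion is at most about 1.3 to 3.3 percentage points, in either direction. It is smaller where subjects have another component event, and about 0.2 to 0.4 points if only bleeds after 30 days are affected. These figures cover life-threatening and major bleeding. If minor bleeds count, the base is larger, and the documents do not allow it to be quantified. No confirmatory conclusion of the trial depends on this. It is worth correcting because the remedy is cheap and a reported difference in valve safety would otherwise be hard to interpret.

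**What to change.** Three changes to Section 7.2, Note 2 and the related reporting:

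1. For the life-threatening and major bleeds the CEC already reviews, base the exclusion on CEC adjudication instead of investigator assessment.
2. State which bleeding severities the composite covers. If minor bleeds are meant to count, say who judges them, since they are on neither CEC list.
3. Also report the composite with all such bleeds included regardless of relatedness, by arm, so that a reader can see whether the result turns on the relatedness call.

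The cost is one added judgement for each bleed the CEC already reviews, and one extra table. No new follow-up is needed, and sample size and testing order do not change. If minor bleeds were brought under the CEC as well, its workload would grow, so that should be decided explicitly. If the sponsor prefers to keep investigator relatedness, the third change alone would still show how far the result depends on it.
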